An Open Label Phase 1b Study of Secukinumab in Patients With
Moderate to Severe Papulopustular Rosacea

Study Protocol and Statistical Analysis Plan

NCT03079531

August 15, 2017

An open label phase 1b study of secukinumab in patients with moderate to severe papulopustular rosacea

Principal Investigator: [name] [name]
Associate Professor of Dermatology
Stanford University School of Medicine
[name]
[name]
[contact]
[contact]

Version 08152017

I. Background

Rosacea is a common inflammatory skin disease affecting up to 10% of adults. Despite this, the etiology of rosacea is unclear, although there may be a genetic predisposition (Chang *et al.*, 2015). Currently, there is no cure. Rosacea can lead to scarring, itching, burning, and is associated with anxiety and depression (Moustafa *et al.*, 2015), significantly affecting quality of life.

II. Study Rationale

Rosacea is a common inflammatory skin disease affecting up to 10% of adults. Despite this, the etiology of rosacea is unclear, although there may be a genetic predisposition (Chang *et al.*, 2015). Currently, there is no cure. Rosacea can lead to scarring, itching, burning, and is associated with anxiety and depression (Moustafa *et al.*, 2015), significantly affecting quality of life.

Secukinumab is an antibody that binds to a protein (interleukin (IL)-17A) that is involved in inflammation. When IL-17A is bound to secukinumab, it cannot bind to its receptor, thereby inhibiting its ability to feed the inflammatory response. In clinical trials, secukinumab has been effective for moderate to severe psoriasis (Blauvelt *et al.*, 2015). Recently, human data from all types of rosacea have shown Th1/Th17 polarization profile of the T-cell response, suggesting that anti-IL-17 therapy may be beneficial for rosacea (Buhl *et al.*, 2015). Hence, secukinumab could be effective against rosacea. This proposal is a proof-of-concept study to use secukinumab in open label design for moderate to severe papulopustular rosacea.

III. Objective and endpoints

Primary objective:

To assess whether secukinumab can reduce the number of papules and/or pustules in moderate to severe papulopustular rosacea after 16 weeks of use.

Secondary objective 1: To assess whether secukinumab can reduce the number of papules and/or pustules in moderate to severe papulopustular rosacea after 12 weeks of use.

Secondary objective 2: To assess whether secukinumab can reduce the overall severity of rosacea by global assessment combining patient reported symptoms and clinical inspection.

Secondary objective 3: To assess whether secukinumab can reduce on erythema in patients with moderate to severe papulopustular rosacea after 16 weeks of use.

Secondary objective 4: To assess whether secukinumab can significantly improve quality of life measures in patients with moderate to severe papulopustular rosacea after 16 weeks of usage.

Secondary objective 5: To assess whether secukinumab leads to any adverse events \geq grade 3 in rosacea patients during the 16 weeks of the study.

Secondary objective 6: To assess whether secukinumab leads to any changes in immune infiltrate in papulopustular rosacea lesions after 16 weeks.

Secondary endpoint 1: Change in the number of papulopustular lesion count on the face due to rosacea before and after 12 weeks of secukinumab.

Secondary endpoint 2: Change in composite global assessment of rosacea using the clinical scorecard measures as shown in Appendix 2.

Secondary endpoint 3: Change in the area of involvement of erythema on the face due to rosacea before and after 16 weeks of secukinumab, as assessed by blinded and independent

photographic assessor using the visual scale in Appendix 3.

Secondary endpoint 4: Change in any of the quality of life scores before and after 16 weeks of secukinumab using the questionnaire in Appendix 4.

Secondary endpoint 5: Describe the incidence and severity of adverse events while on secukinumab for rosacea from baseline to week 16.

Secondary endpoint 6: Describe and quantitate changes in the level and composition of the peri-follicular immune infiltrate in rosacea lesions before and after 16 weeks of secukinumab.

IV. [Study design](#)

This is an open label single arm study whose primary objective is to assess whether secukinumab can significantly reduce the number of papule/pustules after 16 weeks of use. After Stanford Human Subjects Panel approval and written Informed Consent, study participants will use secukinumab 300 mg weekly x 5 weeks (Dose at Week 0, 1, 2, 3, and 4) followed by 2 additional monthly injections (a total of seven 300mg doses), according to the Visit Table. Adverse events will be graded and recorded according to Common Terminology Criteria for Adverse Events (CTCAE) Version 4.0. To avoid investigator bias, a board certified dermatologist blinded to the before or after status of the participant will assess the facial photographs for papulopustule count and erythema. As this is not a crossover study, participants are certainly at risk for reporting bias, however, future larger studies may address this issue. (Because rosacea takes at least 16 weeks to reach maximal clinical response, a crossover study with washout between treatment intervals would be estimated to take 28 weeks, which is a long duration for an exploratory study.) Study participants will follow the procedures as outlined in the Visit Table. Our team has experience administering rosacea quality of life surveys (Chang *et al.*, 2012).

Biomarkers for response such as type and degree of inflammatory infiltrate before and after treatment (16 weeks) will be assessed from 4 mm Keyes punch biopsies of rosacea papules. The tissue will be fixed in formalin and embedded in paraffin for staining with hematoxylin and eosin. Histological assessments will be made by a dermatopathologist blinded to the before or after treatment status of the tissue assessed. Severity of inflammation will be assessed using a 5 point Likert scale, and the numbers of neutrophils, lymphocytes and Langerhans cells will be assessed in a high powered field.

V. Patient population

Adults (N=24) with moderate or severe papulopustular rosacea who meet the eligibility criteria as outlined below.

Key inclusion criteria

- 1) *Moderate to severe papulopustular rosacea defined clinically using the grading system of Wilkin et al. (2004) as having at least ten lesions (either papules or pustules) on face at time of enrollment*
- 2) *Age 18 years or greater*
- 3) *Willing and able to understand and sign informed consent form*

Key exclusion criteria

- 1) *Known hypersensitivity to secukinumab*
- 2) *Topical or oral anti-rosacea medication usage for 28 days prior to enrollment*
- 3) *Active Crohn's disease, as secukinumab may exacerbate this disease*

- 4) *Active infection including tuberculosis, hepatitis B or C, human immunodeficiency virus*
- 5) *Participants with latent tuberculosis will need to have treatment initiated prior to starting study drug*
- 6) *Pregnant or lactating*
- 7) *Active and/or uncontrolled medical conditions that may interfere with study procedures or obscure rosacea assessment such as cutaneous lupus*
- 8) *Use of retinoids within past 4 weeks of enrollment.*
 - a. *Use of topical retinoids within past 3 months of enrollment is allowed if the regimen is stable for 1 month prior to enrollment and subject agrees to keep regimen unchanged for duration of study*
- 9) *Use of antibiotics within 4 weeks of enrollment*
- 10) *Use of light based or laser treatment to face within 8 weeks of enrollment*
- 11) *Use of systemic steroids within 4 weeks of enrollment*
 - a. *Use of topical steroids is allowed if the regimen is unchanged for 2 weeks prior to enrollment and is unchanged for the duration of the study*
- 12) *Acne conglobate, acne fulminans, chloracne, severe acne requiring systemic treatment*

VI. Treatment

This is an open label study using secukinumab 300 mg subcutaneously weekly x5 weeks (Dose at Week 0, 1, 2, 3, and 4) then monthly x2 months (a total of seven doses of 300mg).

VII. Drug administration

Subcutaneous injection

VIII. Dosing guidelines

This study will use a flat dose that is the FDA approved dose for psoriasis (see Package Insert)

IX. Visit schedule and Assessments

Visit 1 (Week -4 to Baseline)

Following written informed consent, a past medical history, concomitant medications, and physical examination will be performed. Vitals signs will be taken and peripheral blood draw will be performed to assess for blood counts, kidney function, and tuberculosis exposure (See Study Calendar).

Visit 2 Week 0 (Baseline)

After verification of eligibility, participants will undergo vital signs, physical examination, adverse event determination, concomitant medication review, photography, skin biopsy and questionnaire administration. Biopsy will be sent for histology and immunohistochemistry. Study drug will be dispensed with a study diary and instructions on self administration.

Visit 3 Week 4

Adverse events and concomitant medication changes will be ascertained. Drug diary will be reviewed for correct study agent usage. Unused drug and sharps containers will be collected. Vitals signs and physical examination will be performed and photographs taken. Rosacea Questionnaire will be administered. Study drug will be dispensed.

Visit 4 Week 12

Adverse events and concomitant medication changes will be ascertained. Drug diary will be reviewed for correct study agent usage. Unused drug and sharps containers will be collected. Vitals signs and physical examination will be performed and photographs taken. Rosacea Questionnaire will be administered. Study drug will be dispensed.

Visit 5 Week 16 (End of treatment)

Adverse events and concomitant medication changes will be ascertained. Drug diary will be reviewed for correct study agent usage. Unused drug and sharps containers will be collected. Vitals signs and physical examination will be performed and photographs taken. Rosacea Questionnaire will be administered. Biopsy will be performed and sent for histology and immunohistochemistry.

Evaluation schedule:

TABLE OF VISITS

Visit number	1	2	3	4	5
Time of Visit	Week -4 to BL	W0 (BL)	W4	W12[‡]	W16[‡]
Inclusion/Exclusion criteria	X	X			
Information & Informed consent	X				
Vital signs	X	X	X	X	X
Physical examination	X	X	X	X	X
Lab test: CBC, MetC, UA	X	X ^{**}			X
Quantiferon	X				
Dispense study medication		X	X	X	
Self-administration of study drug		X [*]	X	X	
Adverse events		X	X	X	X
Concomitant medications evaluation	X	X	X	X	X
Rosacea clinical assessment (Appendix 1-3)	X	X	X	X	X
Facial photography		X	X	X	X
RoseQOL questionnaire (Appendix 4)		X	X	X	X
Skin Biopsy		X			X
Histology & immunohistochemistry		X			X

*In addition to self-administration at the study site at baseline (BL) under study staff supervision, study participants will be provided with three additional doses and a sharps container for weekly self-administration at home. Study participants will be asked to fill out a study diary to assess for compliance and adverse events.

[‡]Week 16 time point was selected to compare the primary endpoint of papule and pustule count with baseline due to previous studies suggesting this time point is needed to achieve significant differences in papule and pustule count using systemic anti-inflammatory treatment with doxycycline (Theobald *et al.*, 2007) and the 16 week time period observed for maximal therapeutic impact for secukinumab in psoriasis. (Langley *et al.*, 2014) We also include a 12 week time point to assess for therapeutic benefit as another study (Sanchez *et al.*, 2005) indicated that this time period is sufficient to detect therapeutic benefit using another systemic agent for rosacea, doxycycline.

** If screening labs within 7 days of baseline, can use screening labs as baseline labs

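### If the Week 0 punch biopsy lies within the photographed face, its mark may reveal before/after status to the blinded photograph reader

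*Combined protocol and SAP*

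**What the plan says.** Section IV describes a single-arm, open-label study and gives one measure against investigator bias in the clinical readings: "a board certified dermatologist blinded to the before or after status of the participant will assess the facial photographs for papulopustule count and erythema". Secondary endpoint 3 (erythema at 16 weeks) likewise relies on a blinded and independent photographic assessor.

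The same section takes tissue before treatment and at 16 weeks from "4 mm Keyes punch biopsies of rosacea papules". No body site is given. The first inclusion criterion defines the disease "as having at least ten lesions (either papules or pustules) on face at time of enrollment", and secondary endpoint 1 counts lesions on the face.

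Section IX gives the procedures at each visit. For Week 0 the list runs "concomitant medication review, photography, skin biopsy and questionnaire administration". For Week 16 the photographs come first and the last item is "Biopsy will be performed and sent for histology and immunohistochemistry". The Table of Visits schedules facial photography at Weeks 0, 4, 12 and 16, and biopsy at Weeks 0 and 16.

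The documents describe no masking or cropping of the biopsy site, no requirement that it lie outside the photographed area, no random order of images and no check on whether the blinding held.

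**The concern.** The reader is meant not to know whether an image comes from before or after treatment. A biopsy taken just after the baseline photograph can leave something on the skin that is absent from that photograph and present in later ones. That is a cue to exactly the information being withheld.

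The lesion count and the erythema grade are both judgements. In a before/after design with no control arm, any tendency to read recognised later images more favourably goes straight into the estimated effect. The cue concerns the whole image, so it bears on erythema as well as on the count.

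**Working it through.** **Step 1. Which photographs could carry the mark.** Inputs: the visit text in section IX and the Table of Visits.

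- Order as listed (photograph, then biopsy): no mark at Week 0; a possible mark at Weeks 4, 12 and 16. The Week 16 biopsy follows the Week 16 photographs, so it adds nothing to them.
- Order reversed at Week 0 (the text is a list, not an explicit sequence rule): a fresh wound in the Week 0 image and a healing site later. The baseline image is still distinguishable.

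Either way the cue separates before from after. It does not separate Weeks 4, 12 and 16 from one another.

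**Step 2. Is the site in the frame?** The biopsied lesions are rosacea papules, and both eligibility and the lesion count concern the face. No other body site is mentioned. A facial site is therefore a reasonable inference, but it remains an inference.

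**Step 3. The plan's own figure.** Section 11 gives a difference of 2 lesions (20% of 10), SD 3, two-sided alpha 0.05, power 0.80 and n = 20.

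- Normal approximation: n = [3 × (1.960 + 0.842) / 2]² = 17.7, so 18.
- Paired t-test, taking 3 as the SD of the change: noncentrality = (2/3) × √20 = 2.98, power 0.807. At n = 19 the power is 0.785, so 20 is the smallest sufficient n.

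The stated 20 reproduces and is not in dispute.

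**Step 4. Illustration of what a cue could do.** Suppose there is no true change and the reader's average count on later images is lower by b lesions. The value of b is an assumption; nothing in the documents supplies it. With n = 20, SD 3 and two-sided alpha 0.05, the noncentrality is (b/3) × √20.

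| Assumed b (lesions) | Share of the planned 2 | Chance of a significant result |
|---|---|---|
| 0 | 0% | 5.0% |
| 0.25 | 12.5% | 6.4% |
| 0.5 | 25% | 10.9% |
| 1 | 50% | 29.4% |
| 2 | 100% | 80.7% |

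At the entry count of 10, b = 0.5 to 1 is an under-count of 5% to 10% (0.05 × 10 = 0.5; 0.10 × 10 = 1). Because b is an average over patients, a 1-lesion shift confined to half of them gives b of about 0.5 × 1 = 0.5.

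**Step 5. The biopsied papule itself.** The punch removes a papule. If that papule is in the baseline count and does not recur, it is 1 of 10 lesions at the entry minimum (10%), or half of the planned 2-lesion difference. The documents do not say how it is counted. This matters for the design of the remedy.

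**The case against.** The strongest case against is that several links are not in the documents. The biopsy site is not stated. The photograph-then-biopsy order is only list order. Nothing says how visible a 4 mm punch mark is in a facial photograph. The lesion and erythema endpoints that name a time point use Weeks 12 and 16, not Week 4, when the mark would be freshest. A face with at least ten lesions, in a disease that section I says can scar, may not make one small mark distinctive, and the documents do not say that images are read in pairs. The study is also a 24-patient proof of concept.

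Most of this stands, and it limits the wording: the mark may reveal status. The order argument does not remove the concern, because the reverse order leaves a cue too.

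A reader might infer more than the documents support:

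- That the blinding is certainly broken. Site and visibility are both unknown.
- That the photograph reader is as exposed to expectation as the treating investigator. Recognising a mark in some patients is not the same as knowing every time point for all of them, and the erythema assessor is specified as independent.
- That nothing else could show a discrepancy. The Table of Visits schedules a clinical rosacea assessment using Appendices 1 to 3 at every visit, so a parallel reading exists, although no blinding is described for it.
- That a 5% to 10% under-count has been shown. It is an assumption, and the 25% to 50% share follows from it whatever the cause of the shift.

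**Conclusion.** The point holds as a conditional one. If the Week 0 biopsy is on the face within the photographed area, following the plan as written can leave a before/after cue in the images used for the lesion count and for erythema, and the plan contains no step to remove it. The blinding at risk is the only stated protection against investigator bias for those readings.

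The size cannot be derived from the documents. As an illustration, an average reader shift of 0.5 to 1 lesion would be 25% to 50% of the planned difference. With no true change, it would raise the chance of a significant result from 5% to between 10.9% and 29.4%. This rests on the assumed shift, an SD of the change of 3 and 20 evaluable patients. The point does not alter the sample size. It is worth acting on because the remedy is cheap, not because bias has been demonstrated.

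**What to change.** Record the biopsy site for each patient. Before any reading, cover it with an identical opaque mask in every image of that patient, including Week 0. Remove dates and present the images in random order. Count lesions and grade erythema outside the mask only. If the Week 16 photographs could be taken after the second biopsy, mask that site in the same way.

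State in section 11 that the photographic baseline count excludes the biopsied lesion, and keep this count separate from the one used for eligibility. A patient who enters with 10 lesions would then have a photographic baseline of 9, and the 2-lesion planning difference, which is built on 10, should be read with that in mind. The same rule prevents removal of the papule by the biopsy from being scored as improvement.

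The cost is image preparation by existing staff, with no added visit, procedure or reader. The losses are a small unread patch of skin, the same at every time point, and the biopsied papule from each count. Masking can also be applied to photographs already taken, provided they have not yet been read.

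### If the Week 0 biopsy takes a counted facial papule, the single-arm fall in lesion count is overstated by 0 to 1 lesion per patient, and no analysis allows for it

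*Combined protocol and SAP*

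**What the plan says.** Section IV (Study design) describes one open-label arm. Biomarkers "will be assessed from 4 mm Keyes punch biopsies of rosacea papules", before treatment and at 16 weeks. The same section says that "a board certified dermatologist blinded to the before or after status of the participant will assess the facial photographs for papulopustule count and erythema". That points to the photographs as the source of the count, although the Table of Visits also schedules a "Rosacea clinical assessment (Appendix 1-3)" at every visit.

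Section IX gives the Week 0 activities as a list: "participants will undergo vital signs, physical examination, adverse event determination, concomitant medication review, photography, skin biopsy and questionnaire administration". For Week 16 it reads "photographs taken. Rosacea Questionnaire will be administered. Biopsy will be performed and sent for histology and immunohistochemistry". Photography is therefore listed before biopsy at both visits.

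The footnote to the Table of Visits states that the "Week 16 time point was selected to compare the primary endpoint of papule and pustule count with baseline". Secondary endpoint 1 in section III is "Change in the number of papulopustular lesion count on the face due to rosacea before and after 12 weeks of secukinumab".

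Section 11 sizes the study on a fall of 2 lesions, which is 20% of the entry minimum of 10. It assumes an SD of 3, two-sided alpha of 0.05 and power of 0.80, and arrives at 20 patients, with 24 enrolled. Smaller falls are described as not clinically meaningful.

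No section gives the body site of the biopsy, asks for the sampled papule to be recorded, or says how it is handled in the counts.

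**The concern.** A punch biopsy of a papule physically removes a lesion of the type being counted. If it is taken from the face after the baseline photographs, the lesion appears at baseline and cannot appear at Week 12 or Week 16, whatever the drug does. The Week 16 biopsy is listed after the Week 16 photographs, so it does not offset the first. Blinding the reader does not help, because the lesion really is absent. A randomised comparison would cancel the effect, since both arms would be biopsied. Here the before-and-after difference is the whole result.

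One lesion is not negligible on this plan's scale. It is half of the 2-lesion target at a count of 10. As a share of the baseline count it is 10% at 10, 6.7% at 15 and 5% at 20. The Week 12 count is exposed in the same way.

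**Working it through.** **Inputs from section 11.** Fall of 2 lesions, SD 3, two-sided alpha 0.05, power 0.80, 20 evaluable patients.

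**Assumptions not in the documents.** One facial papule is biopsied per patient, after the baseline count. SD 3 is the SD of the within-patient change. The biopsy affects only the sampled lesion and leaves that SD unchanged. p is the share of biopsied papules that would otherwise have been counted at the later visit, from 0 to 1.

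**1. The plan's own figure.** One-sample t-test on the change, noncentrality = difference × √n / SD. For n=20: 2 × √20 / 3 = 2.98, critical t (19 df) = 2.093, power 0.807. For n=19 the power is 0.785. The smallest adequate n is 20, as stated, so reading SD 3 as the SD of change fits the plan.

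**2. Size of the shift.** Let the baseline count be N and let the count without biopsy fall by D. With the biopsy, the later count averages N − D − p.
- Full count: N − (N − D − p) = D + p. The fall is overstated by p.
- Biopsied lesion subtracted from baseline: (N − 1) − (N − D − p) = D − (1 − p). The fall is understated by 1 − p.

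With a stable count (D=0) and lost lesions replaced elsewhere, the first shows a false fall of p and the second a false rise of 1 − p. The two differ by exactly 1, and the true value lies between them.

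**3. Chance of a significant reduction with no drug effect.** n=20, full count, upper tail of the same test with the difference set to p:

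| p | SD 3 | SD 4.24 |
|---|---|---|
| 0 | 2.5% | 2.5% |
| 0.25 | 5.4% | – |
| 0.5 | 10.5% | 7.2% |
| 0.75 | 18.5% | – |
| 1 | 29.3% | 16.9% |

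SD 4.24 = 3 × √2 applies if 3 were the SD of each count and the two counts were uncorrelated. At an assumed SD of 5, the p=1 figure is 13.3%. The smallest significant mean fall at SD 3 is 2.093 × 3 / √20 = 1.40 lesions, so a shift of at most 1 could not by itself give a significant result in a sample with exactly that mean and SD. It raises the chance that sampling variation does the rest.

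**4. Power of the subtracted analysis when the drug works.** If the full count would truly fall by 2, this analysis sees 2 − (1 − p) = 1 + p, where p is now persistence on drug.
- p=0.8 (each lesion equally likely to clear, none new): fall 1.8, noncentrality 2.68, power 0.721.
- p=0.5: fall 1.5, noncentrality 2.24, power 0.56.
- p=0: fall 1, noncentrality 1.49, power 0.29.

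The plan's 0.807 is the reference for an unshifted 2-lesion fall.

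**The case against.** The strongest reply is that every link is inferred. The site is not stated, the Week 0 text is a comma list rather than a sequence, and nothing in the documents says how long an untreated papule lasts. If most papules would have gone by Week 16, p is near 0 and there is little to correct. A residual mark misread as a papule would push the other way, so even the direction is not certain. This stands as a limit on size and confidence, and it is why the point is conditional. It does not remove the point. Facial lesions define both eligibility and the count, nothing directs the biopsy elsewhere, and the plan's silence is what needs to be filled.

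A second reply concerns the remedy. Dropping the biopsied lesion and its site from every count looks like the natural cure, but it selects a site because it held a lesion at baseline, while new lesions arise elsewhere. By step 2 it biases the result against the drug by 1 − p. For p below 0.5 that is a larger error than the one being corrected. This objection holds in full, so exclusion at every visit should not be the primary analysis.

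Third, this is a proof-of-concept study, and section 11 uses the 20% figure to size it, not as a success rule for each patient. That is fair, and it lowers the priority. The plan does still propose a powered significance test in one arm.

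**Conclusion.** The point holds in conditional form. If the Week 0 papule is facial and is taken after the baseline count, the recorded falls at Weeks 12 and 16 are overstated by 0 to 1 lesion per patient, and the plan has no analysis that would show it. With no drug effect, n=20 and SD 3, the chance of a significant reduction rises from 2.5% to at most 29.3%, or 16.9% at SD 4.24. p may differ between the two visits.

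A reader might infer more than the documents support:
- 29.3% is not the expected error rate. It needs every biopsied papule to have otherwise persisted, and no value of p is favoured.
- The sample size is not wrong; 20 reproduces.
- The biopsy site might reveal the time order to the photograph reader, but its visibility at Week 16 is not documented, so nothing here rests on that.

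The change is a cheap improvement. Confidence is medium, because site, sequence and lesion turnover are all unstated.

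**What to change.** Add a few sentences to sections IX and 11:

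1. State the body site of the biopsy, and that photographs and any clinic count precede it at Weeks 0 and 16.
2. Record which papule was biopsied at Week 0, at the time, since this may not be recoverable later.
3. Keep the full count as the primary analysis.
4. Prespecify a sensitivity analysis for Weeks 12 and 16 in which the recorded lesion, where it was facial and counted, is subtracted from the baseline count.
5. Report the two as bounds, and call a reduction robust to the biopsy only if it holds in both. Note that the bounds assume the healed site is not scored as a papule.

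Eligibility, the 2-lesion target and the sample size stay as they are. The cost is one recorded item and one extra analysis, with no added visit or procedure. The downside is that the sensitivity analysis is conservative: for a true 2-lesion fall its power is 0.721 at p=0.8 and 0.56 at p=0.5. Failing it would therefore not show that the drug has no effect, and the report should say so.
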